### **12.2.4 Objective response rate**

The ORR will be based on the programmatically derived RECIST using the BICR data. The ORR will be compared between MEDI4736 versus placebo using a Fisher's exact test. A binary response variable for ORR will be used for the analysis with the categories of CR and PR versus SD, PD and NE. The results of the analysis will be presented in terms of the proportion of responders and a p-value.

This analysis of ORR will be repeated using the results of the programmatically derived PFS using the site Investigator data from all scans based upon RECIST as a sensitivity analysis to confirm the results of the primary analysis derived from the CRFs. An additional sensitivity analysis will be performed on ORR using BICR tumour data based upon RECIST modified for confirmation of progression to determine if there is any difference when using progression confirmation rules. Finally, an exploratory analysis of ORR using the irRC data obtained from the BICR will be performed where the above analysis will be repeated.

Summaries will be produced that present the number and percentage of patients with a tumour response (CR/PR). Overall visit response data will be listed and summarised over time for all patients (ie, the FAS). For each treatment arm, best objective response (BoR) will be summarised by n (%) for each category (CR, PR, NED, SD, PD, NE). No formal statistical analyses are planned for BoR.

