1.2 Study Design

This study is a Phase III, randomised, double-blind, placebo-controlled, multi-centre study assessing the efficacy and safety of MEDI4736 compared with placebo as sequential therapy in male and female patients with locally advanced, unresectable non-small cell lung cancer (NSCLC) (Stage III) who have not progressed following definitive, platinum-based, concurrent chemoradiation therapy.

Approximately 880 patients with locally advanced, unresectable NSCLC (Stage III) will be recruited and 702 patients randomised at 260 to 330 sites in Australia, Asia, Europe, North and South America and South Africa. These patients will be in complete response (CR), partial response (PR), or have stable disease (SD) following definitive, platinum-based, concurrent chemoradiation therapy.

Patients will be randomised in a 2:1 ratio (MEDI4736 to placebo) to 1 of 2 arms:

- MEDI4736 (10 mg/kg Q2W iv for up to 12 months).
- Placebo (matching placebo for infusion Q2W iv for up to 12 months).

Randomisation will be stratified by: age at randomisation (<65 vs ≥65 years of age), sex (male vs female), and smoking history (smoker vs non-smoker). Patients must not have progressed following definitive, platinum-based, concurrent chemoradiation therapy; radiation therapy must be completed within 1 to 42 days prior to randomisation in the study (the last dose of radiation therapy is defined as the day of the last radiation treatment session). For patients who are recovering from toxicities associated with prior treatment, randomisation may be delayed by up to 42 days from the end of the chemoradiation therapy. For those patients randomised to the placebo arm no cross-in to the MEDI4736 arm is permitted and similarly those patients randomised to the MEDI4736 arm no cross-in to the placebo arm is permitted.

Administration of study drug will commence on Day 1 following randomisation to MEDI4736 or placebo after confirmation of eligibility and will continue on a Q2W schedule for a maximum duration of 12 months. Study drug should be discontinued prior to 12 months if there is confirmed PD (unless the investigator considers the patient continues to receive benefit from the study drug), initiation of alternative cancer therapy, unacceptable toxicity, withdrawal of consent, or other reasons to discontinue study drug occur.

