3.2.2.2 Objective response rate

ORR (per RECIST 1.1 as assessed by the BICR) is defined as the number (%) of patients with at least 1 visit response of CR or PR and will be based on a subset of all randomised patients who have measurable disease at baseline per BICR. If the selected reviewer did not consider that a patient has measurable disease then this patient should not contribute to the denominator.

Data obtained up until progression, or the last assessment in the absence of progression, will be included in the assessment of ORR. Patients who go off treatment without progression, receive a subsequent therapy and then respond will not be included as responders in the ORR.

ORR will also be obtained using the algorithm described above for the RECIST site investigator data. The denominator for ORR will be all randomised patients with measurable disease at baseline per the site investigator (ie, the ITT population).

Additionally, ORR will be obtained using the algorithm described above from the RECIST BICR data, but following a modification where any objective progression requires confirmation. Therefore, data obtained up until confirmed progression (ie first progression date that is subsequently confirmed), or the last assessment in the absence of a confirmed progression, will be included in the assessment of ORR. Note that the response may be after an unconfirmed progression.

For exploratory purposes, ORR will also be obtained for the irRECIST 1.1 data provided by BICR.

Best objective response

Best objective response (BoR) is calculated based on the overall visit response from each RECIST assessment. It is the best response a patient has had following randomisation but prior to starting any subsequent cancer therapy and prior to RECIST progression or the last assessment in the absence of RECIST progression and subsequent cancer therapy.

Categorisation of BoR will be based on RECIST using the following response categories: CR, PR, SD, PD and NE.

BoR will be determined programmatically based on RECIST from the overall visit response at each visit using BICR data including all data up until the first progression, the start of any subsequent cancer therapy or the last assessment in the absence of progression.

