4.1.2 Multiplicity

The multiple testing procedure will define which significance levels should be applied to the interpretation of the raw p-values for the 2 primary endpoints of PFS and OS and the key secondary endpoints of OS24 and ORR.

There will be 4 DCO time points in the study. The DCO for the interim PFS analysis (first analysis) will be done when 367 PFS events have occurred (52% maturity), approximately 30 months after the first patient is randomised. The DCO for the primary PFS analysis (second analysis) and interim OS analysis will be done when at least 458 PFS events have occurred

(65% maturity) at approximately 36 months after first patient is randomised. It is expected that approximately 285 death events (41% maturity) will be available for the interim OS analysis. The third analysis data cut-off will occur at the time of the second OS interim analysis when it is expected that 393 OS events have occurred (56% maturity, approximately 47 months after the first patient is randomised). The DCO for the primary OS analysis (fourth analysis) will be done when 491 OS events have occurred (70% maturity) at approximately 62 months.

The overall 5% type 1 error will be split between the co-primary endpoints OS and PFS. An alpha level of 2.5% will be allocated to OS analysis and an alpha level of 2.5% will be allocated to the PFS analysis. An interim PFS analysis for superiority will occur when approximately 367 PFS events have occurred and the primary PFS analysis will be performed when 458 PFS events have accumulated. The 2.5% alpha level allocated to PFS will be controlled at the interim and primary time point by using the Lan DeMets ([Lan and DeMets 1983](#)) spending function that approximates an O'Brien Fleming approach, where the significance level applied at the interim depends upon the proportion of information available. If 80% of the PFS events required at the time of the primary PFS analysis is available at the time of the interim (i.e., 367/458 PFS events have occurred), the 2-sided significance level to be applied for the PFS interim analysis would be 1.04% and the 2-sided significance level to be applied for the primary PFS analysis would be 2.19%.

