If the testing for PFS is not significant at either the interim ($\alpha=1.04\%$) or at the primary analysis ($\alpha=2.19\%$), the OS will be tested at the levels specified in [Figure 2](#). In this case if the testing for OS is significant at any interim analysis or primary analysis the full 2.5% alpha level for OS can be propagated to the testing of PFS, which means that the PFS will be tested at an overall alpha level of 5%. Following GSHf, the alpha level for the interim analysis of PFS will not be changed but the alpha level for the primary analysis of PFS will be recalculated based on 5% alpha level overall with interim alpha levels as specified in [Figure 2](#). For example, if the information fraction for the interim analyses is as specified (80% for PFS interim and 58%/80% for OS interim) the alpha level for the primary PFS analysis will be 4.88%, given testing of OS is significant at interim ($\alpha=0.21\%$ and 0.98%) or at primary analysis ($\alpha=2.17\%$). The alpha level for the interim PFS analysis will remain at 1.04%.

OS24 and ORR will not be tested unless the null hypotheses for both PFS and OS are rejected according to the GSHf procedure described above. After both PFS and OS are rejected the OS24 will be tested with 5% alpha level controlled at the interim and primary time point. The interim analyses of OS24 will use the same interim alpha level for OS at the same analysis point. The alpha for primary analysis of OS24 will be calculated based on interim alpha levels and information fractions at the interim so that the alpha level for OS24 is controlled at 5% overall. ORR will only be tested after the null hypothesis of PFS, OS, and OS24 are all rejected and ORR will be tested at a 5% level.

The FWER is strongly controlled at 5% for PFS and OS according to [Ye et al 2012](#). The FWER for PFS, OS, and OS24 is also strongly controlled at 5% due to the fix-sequence testing nature and according to [Glimm et al 2009](#). Finally the FWER is still strongly controlled after adding the fix-sequence testing of ORR. So the FWER is strongly controlled at 5% for the testing of all four endpoints. [Figure 2](#) shows the multiple testing framework.

Figure 2 Multiple testing procedures for controlling the type 1 error rate

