Objective Response Rate	Fisher’s exact test using BICR data (RECIST 1.1) Sensitivity analysis using the Fisher’s exact test using site investigator tumour data (RECIST 1.1) Sensitivity analysis using the Fisher’s exact test using BICR tumour data (RECIST 1.1, modified for confirmation of progression) Exploratory analysis using the Fisher’s exact test using BICR tumour data (irRECIST)
Duration of Response	Analysis following the method described by Ellis et al 2008 using BICR tumour data (RECIST 1.1)
Proportion of patients alive and progression free at 12 and 18 months	Kaplan Meier estimates of progression free survival at 12 and 18 months
Time from randomisation to second progression	Stratified log-rank test
Time to death or distant metastasis	Stratified log-rank test using site BICR tumour data (RECIST 1.1)

Table 8 Formal statistical analyses to be conducted and pre-planned sensitivity analyses

Endpoints Analysed	Notes
Symptom improvement rate (EORTC QLQ-C30 and LC13 endpoints)	Logistic regression
HR QoL/Function improvement rate (EORTC QLQ-C30 endpoints)	Logistic regression
Time to HR QoL/Function deterioration (EORTC QLQ-C30 endpoints)	Stratified log-rank test
Time to symptom deterioration (EORTC QLQ-C30 and LC13 endpoints)	Stratified log-rank test
Change from baseline (EORTC QLQ C30 and LC13; EQ-5D-5L health state utility values and Visual Analogue Scale)	Mixed model repeated measures analysis

BICR Blinded Independent Central Review; EORTC QLQ-C30 European Organisation for Research and Treatment of Cancer 30-item core quality of life questionnaire; EQ-5D-5L EuroQoL 5 dimension, 5 level health state utility index; irRC Immune-related response criteria; LC13 Lung Cancer Module; HR QoL Quality of Life; RECIST Response Evaluation Criteria In Solid Tumours.

All outputs will be summarised by treatment arm as randomised for all ITT patients.

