4.2.2.2 Objective response rate

The ORR will be based on the programmatically derived RECIST outcome using the BICR data. The treatment comparison of ORR will be based on a Fisher's exact test using mid p-values. A binary response variable for ORR will be used for the analysis with the categories of CR and PR vs SD, PD and NE. The results of the analysis will be presented in terms of the proportion of responders and a p-value.

The mid-p-value modification of the Fisher exact test amounts to subtracting half of the probability of the observed table from Fisher's p-value.

$$\text{Fisher's exact test mid p-value} = \text{Two sided p-value} - \frac{\text{Table probability}}{2}$$

This analysis of ORR will be repeated using the results of the programmatically derived outcome using the site investigator data based upon RECIST as a sensitivity analysis to confirm the results of the primary analysis based on the site investigator tumour data. An additional sensitivity analysis will be performed on programmatically derived outcomes using BICR tumour data based upon RECIST modified for confirmation of progression to determine if there is any difference when using progression confirmation rules. Finally, an exploratory analysis of ORR using the irRECIST 1.1 data obtained from the BICR will be performed where the above analysis will be repeated.

Summaries will be produced that present the number and percentage of patients with a tumour response (CR/PR) based upon the number of patients with measurable disease at baseline per BICR or investigator as appropriate (see Section 3.2.2.2). For each treatment arm, best objective response (BoR) will be summarised by n (%) for each category (CR, PR, ND, SD, PD, NE). This will be produced for the BICR of RECIST only. No formal statistical analyses are planned for BoR.

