4.2.3.1 EORTC QLQ-C30

Time to symptom deterioration will be analysed for each of the 3 symptom scales (fatigue, pain, nausea/vomiting) and the 5 individual symptom items (dyspnoea, insomnia, appetite loss, constipation, diarrhoea).

Time to HRQoL/function deterioration will be analysed for the 5 function scales (physical, role, emotional, cognitive, and social) and global health status/HRQoL. For treatment comparison, a stratified log-rank test will be used, as described for the primary analysis of OS.

The HR and 95% CI for each scale/item will be presented graphically on a forest plot.

A summary of the symptom improvement rate for each of the 3 symptom scales and the 5 individual symptom items will be produced. Similarly, a summary of HR QoL/function improvement rate for each of the 5 function scales (physical, role, emotional, cognitive, and social) and global health status/HR QoL will be produced. Symptom improvement rate and HR QoL/function improvement rate will be analysed by comparing between treatment arms using a logistic regression model adjusting for the same factors as the co-primary endpoints. The results of the analysis will be presented in terms of an odds ratio (an odds ratio greater than 1 will favour treatment A) together with its associated profile likelihood 95% CI (e.g. using the option 'LRCI' in SAS procedure GENMOD) and p-value (based on twice the change in log-likelihood resulting from the addition of a treatment factor to the model). The odds ratio and 95% CI for each scale/item will be presented graphically on a forest plot. If there are very few responses in one treatment arm, a Fisher's exact test will be considered.

For each of the 3 symptom scales (fatigue, pain, nausea/vomiting), 5 individual symptom items (dyspnoea, insomnia, appetite loss, constipation, diarrhoea), 5 functional scales (physical, role, emotional, cognitive, and social), and global health status/HR QoL, time to deterioration will be presented using a Kaplan-Meier plot. Summaries of the number and percentage of patients experiencing a clinically meaningful deterioration or death, and the median time to deterioration will also be provided for each treatment arm.

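### ORR, a confirmatory key secondary endpoint, is tested without the randomisation strata that the co-primary tests use; the test is valid, and the possible power gain from stratifying is small

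*SAP*

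**What the plan says.** SAP 4.1.2 sets significance levels "for the 2 primary endpoints of PFS and OS and the key secondary endpoints of OS24 and ORR". ORR comes last: PFS, OS and OS24 must all be "rejected and ORR will be tested at a 5% level". It is therefore inside the family for which the SAP claims strong error control.

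The ORR test is Fisher's "exact test using mid p-values. A binary response variable for ORR will be used for the analysis" (SAP 4.2.2.2). SAP Table 8 and protocol 12.2.4 also name Fisher's test, without the mid-p modification. None of the three mentions strata or covariates, and the ORR sensitivity and exploratory analyses repeat the same test. The denominator "will be based on a subset of all randomised patients who have measurable disease at baseline per BICR" (SAP 3.2.2.2); its size is not given.

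SAP 1.2 states: "Randomisation will be stratified by: age at randomisation", sex and smoking history, with 2:1 allocation. Protocol 5.2.1 adds that there is one blocked list per stratum.

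Elsewhere the factors are used:
- OS and PFS: stratified log-rank tests (SAP 4.2.1.1, 4.2.1.2).
- PFS2 and TTDM: the PFS methods with the same covariates (SAP 4.2.2.6, 4.2.2.7).
- PRO improvement rates, which are binary and outside the main testing procedure: compared "using a logistic regression model adjusting for the same factors as the co-primary endpoints" (SAP 4.2.3.1).

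For OS24, SAP 4.2.2.1 gives a formula for combining strata but does not say outright that the stratified version is the confirmatory one.

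**The concern.** Stratified randomisation balances the arms within strata, so the true variance of the difference in response rates no longer contains the between-stratum part. An unstratified test still charges for it. If the strata predict response, the test is then conservative and loses some power.

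The plan already has a stratum-adjusted method for a binary outcome and applies it to the PRO rates, but not to the one binary endpoint that carries confirmatory alpha. No reason is given. At stake is a little power on the last confirmatory hypothesis, and agreement between the analysis and the design. Control of type I error is not at stake.

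**Working it through.** **No ORR figure to reproduce.** The plan states no ORR rate, effect or power. As a check on the design settings used here (2:1, two-sided 2.5%), Schoenfeld's formula gives 96.4% power for PFS (458 events, HR 0.67; stated at least 95%) and 85.2% for OS (491 deaths, HR 0.73; stated at least 85%). Both agree with the plan.

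**Closed-form look at conservatism.** The pooled variance splits as p(1-p) = Σ w_k p_k(1-p_k) + Σ w_k (p_k - p)². If the second term is a share r of the total, the unstratified test has a true level of about 2[1 - Φ(1.96/√(1-r))].

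Protocol 1.1.2.1 quotes, for another anti-PD-L1 antibody, ORR of 26% in smokers and 10% in never smokers, an odds ratio of (0.26/0.74)/(0.10/0.90) = 3.2. Taking those rates at face value for smoking alone:
- 90% smokers (assumed): p = 0.244, r = 0.9 × 0.1 × 0.16² / (0.244 × 0.756) = 1.2%, level about 4.9%.
- 75% smokers (assumed): p = 0.22, r = 0.75 × 0.25 × 0.16² / (0.22 × 0.78) = 2.8%, level about 4.7%.

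So smoking alone, even with that contrast, makes the test only slightly conservative.

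**Simulation.** Assumed inputs: 8 strata with mix 55/45 (age), 70/30 (sex) and 90/10 (smoking); 2:1 within strata; about 420 or 702 measurable patients; placebo ORR 10%, 15% or 20%; common odds ratio 1.9 (treated ORR about 17-32%); the same log-odds difference for each factor (0, 0.5 or 1.0). There were 10,000 replicates per setting at two-sided 5%; the Monte Carlo standard error of a 5% level is √(0.05 × 0.95/10,000) = 0.22 points.

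Mid-p is the two-sided Fisher p minus half the probability of the observed table. With a_k responders among n_1k treated, n_2k placebo patients and s_k responders among n_k in stratum k, the Cochran-Mantel-Haenszel (CMH) statistic is z = Σ(a_k - n_1k s_k/n_k) / √Σ[n_1k n_2k s_k(n_k - s_k) / (n_k²(n_k - 1))].

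| Log-odds per factor | Level, Fisher mid-p | Level, CMH | Power, CMH minus mid-p (points) |
|---|---|---|---|
| 0 | 4.6-5.3% | 4.6-5.3% | -1.2 to -0.3 |
| 0.5 | 4.4-5.3% | 4.6-5.6% | -0.5 to +0.6 |
| 1.0 | 3.9-4.7% | 4.6-5.2% | +1.3 to +3.2 |

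The ends of the range both occur at about 420 patients. With placebo ORR 10% and no prognostic strata, power goes from 54.1% to 52.9%. With placebo ORR 20% and strong strata, it goes from 68.6% to 71.8%.

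**Second set of assumptions** (placebo ORR 18%, odds ratio 1.8, 420 or 600 patients, 75% or 90% smokers). The change in power was:
- +2.7 to +3.4 points with all three factors at 1.0;
- +0.6 to +1.4 with smoking at 1.15 and the other two at 0.5;
- 0 to +0.7 with smoking alone prognostic;
- -0.8 to -0.3 with none prognostic.

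**The case against.** The strongest reply is that nothing is wrong. Fisher's test is prespecified, named in both documents and valid. ORR is last in the sequence and has no planned power to miss. All of that stands, and it limits this point to efficiency and consistency.

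Four further points stand in part:
- **Stratifying is not free.** If the strata do not predict response, it costs about 0.3 to 1.2 points of power.
- **The evidence that they do predict response is thin.** The 26% against 10% comes from treated patients on another antibody with no control arm. It cannot separate a prognostic effect from a larger drug effect in smokers, and it says nothing on age or sex. It is only suggestive.
- **The match to the randomisation is looser than for OS or PFS.** Blocks are formed over all randomised patients, and ORR uses the measurable-disease subset. Balance within strata is approximate there, and some of the eight strata may be small.
- **SAP 4.2.3.1 itself falls back on Fisher's test for PRO rates when one arm has very few responses.** Its use for a binary outcome is therefore not alien to the plan. But there it is the exception, and adjusted logistic regression is the rule.

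A reader might also infer that every other test in the confirmatory family is stratified. The documents support that for OS and PFS. For OS24 they give a stratified formula without committing to it.

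**Conclusion.** The point holds as a minor one. The confirmatory ORR test ignores the randomisation factors that the co-primary tests and even the supportive binary PRO analyses use, and no stratified ORR analysis is planned in either document.

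A reader might infer that the ORR test is invalid or that family-wise error is at risk. Neither follows: the simulated level of the mid-p test was 3.9-5.3%, falling below 5% when the strata are strongly prognostic.

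The effect on power runs from about -1 point (strata not prognostic) to about +3 points (all three strongly prognostic), and is close to zero if smoking alone matters. Every ORR input behind that range is assumed, because the plan gives no response rate, effect size or count of measurable patients.

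**What to change.** In SAP 4.2.2.2, SAP Table 8 and protocol 12.2.4, make the confirmatory ORR comparison a CMH test stratified by age group, sex and smoking as entered in IVRS, the source that SAP 4.2.1.1 already sets for OS. Fix one version of the test before unblinding. A rule to switch to an exact version if the data look sparse would leave the confirmatory test dependent on the data. Keep the Fisher mid-p result as supportive, and use the same wording in all three places. A stratified odds ratio with its confidence interval could be reported alongside, since SAP 4.2.2.2 now gives only responder proportions and a p-value.

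The cost is a short edit, one procedure call, and up to about 1 point of power if the strata turn out not to be prognostic. The protocol synopsis records that the planned analyses had been concluded by Amendment 07. For those analyses the planned Fisher test remains the confirmatory one, and a stratified result could be added only as post hoc support.
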